## 3.0 Reason for amendment

Discrepancy between Protocol inclusion criteria and routine clinical practice.

The Investigators informed that it's impossible to match inclusion criteria that patient should have been taking Omacor for at least 3 days at the time of enrollment into the program (inclusion criteria #3) because patients usually return to the physician not earlier than 1 month after treatment administration.

## 4.0 Changes

The changes were made in the inclusion criteria #3 and corrected throughout the Protocol.

The changes were summarized in the table below:

Section, page	Previous version	New version
6.1.1 Inclusion Criteria, page 8	3. Patients having been prescribed Omacor (Omega-3 triglycerides [EPA/DHA = 1.2/1 - 90%]) for at least 6 months  AND  who have been taking Omacor for 10±7 days at the time of enrollment into the program.	3. Patients having been prescribed Omacor (Omega-3 triglycerides [EPA/DHA = 1.2/1 - 90%]) for at least 6 months  AND  who have been taking Omacor no more than 14 days at the time of enrollment into the program.
6.5 Study Conduct, Figure 1. The program flow-chart, page 12	Patients who have been receiving Omacor for 10 ± 7 days	Patients who have been receiving Omacor no more than 14 days

---

### 3.0 Rationale

This study is a prospective observational program within the frames of which Omacor (Omega-3 triglycerides [EPA/DHA = 1.2/1 - 90%]) is prescribed to patients with a history of myocardial infarction within a routine procedure as a part of the combination therapy (in combination with statins, antiaggregants, beta-blockers, angiotensin-converting enzyme inhibitors (ACE)) and/or to patients with hypertriglyceridemia. The population of observed patients will be limited to those who were prescribed Omacor for the first time or not earlier than 3 months after the last dose of Omacor and course of administration is at least 6 months.

This program is conducted to assess the effectiveness of the use of digital technology tools to enhance the adherence of patients with a history of myocardial infarction and/or hypertriglyceridemia, as well as to assess the impact of the use of digital technology tools on the effectiveness of treatment and improvement of the quality of life of these patients.

The primary objective of the program is to assess patient adherence to therapy with Omacor. Adherence is defined as the extent to which a person's behavior in taking medication corresponds with agreed recommendations from a health care provider (World Health Organization, 2003) that expects patient active involvement into treatment process and strong relationship between patient and physician. In this study adherence rate will be calculated as the sum of days when patient taken the full prescribed dose of Omacor in period divided by the number of days in period.

Secondary objectives include assessment of the reasons for discontinuation of Omacor, assessment of the quality of patients' life and assessment of health outcome during the study.

Additional tasks of the program include a description of the target patient population prescribed with Omacor, as well as raising patients' awareness about the disease.

### 4.0 Study Objective(s)

#### **Primary objective**

1. To assess adherence to therapy with Omacor in post-MI patients or patients with hypertriglyceridemia.

#### **Secondary objectives**

1. To evaluate the reasons for the termination of therapy with Omacor.
2. To evaluate the quality of life of patients during the program.
3. To evaluate health outcomes in patients group during the program.

## Primary endpoints

1. Mean adherence rate at the end of the study (Visit 3).

Adherence rate will be calculated as the sum of days when patient taken the full prescribed dose of Omacor® in period divided by the number of days in period.

2. Mean score of National questionnaire of treatment compliance (edited by Fofanova T.V. et al.) [9] at the end of the study (Visit 3).

## Secondary endpoints

1. The percentage of patients who have chosen each of the suggested reasons for therapy termination.
2. The average score on each of 8 scales of SF-36 quality of life questionnaire at Visit 2 and Visit 3 vs. the baseline (Visit 1).
3. Change of lipid profile parameters at Visit 2 and Visit 3 vs. the baseline (Visit 1).
4. Number of hospitalizations due to cardio-vascular reasons during 6 months of the program.
5. Number of new cases of stenocardia during 6 months of the program.
6. Number of non-fatal myocardial infarction cases during 6 months of the program.
7. Number of cases of cardio-vascular death during 6 months of the program.
8. Mean adherence rate at Visit 2.
9. Change of mean adherence rate by end of the study (Visit 3) versus Visit 2.
10. The percentage of patients with adherence rate  $<0,5$ ,  $0,5-0,7$ ,  $\geq0,8$  at Visit 2 and Visit 3.
11. Mean score of National questionnaire of treatment compliance (edited by Fofanova T.V. et al.) [9] at Visit 1, Visit 2.
12. Change of mean score of National questionnaire of treatment compliance (edited by Fofanova T.V. et al.) [9] at Visit 2 and Visit 3 versus baseline (Visit 1).

## Experimental endpoints

1. The average number of days when Omacor was taken during observational study period of 6 months. The last day of drug product administration is defined as date of last Omacor dose or last subject visit within this program whatever is earlier.
2. Correlation between primary endpoints and patients' social characteristics (gender, age, employment status, education level, marital status).
3. The percentage of patients who assess the drug product usability as very good, good, moderate and poor after 1 month of Omacor treatment.

For endpoints which are applicable, further analysis will be performed in subgroups of patients with the different medication adherence rate: <0,5, 0,5-0,7, ≥0,8 at Visit 2 and Visit 3. Adherence rate will be calculated as the sum of days when patient taken the full prescribed dose of Omacor in period divided by the number of days in period.

Additional objectives of the program include a description of the target patient population prescribed with Omacor, as well as raising patients' awareness about the disease.

#### **4.1.2 Exclusion Criteria**

1. Patients taken medicines (except for Omacor) or nutrition supplements containing omega-3 in any proportions at the time of enrollment into the program  
OR  
it has been less than 3 months since last dose of medicines or nutrition supplements containing omega-3 taken.
2. Female patients during pregnancy or breastfeeding.
3. Patients with increased sensitivity to the active substance, excipients, and soy.
4. Patients with exogenous hypertriglyceridemia (type I hyperchylomicronemia).

5. Participation in any other clinical or non-clinical study/program at present or within the latest 30 days.
6. Patients with any other clinical states that make him/her ineligible for the program on the study doctor's opinion based on clinical assessment.

#### **4.2 Number of Patients to be Enrolled**

In total, the program will include 3000 patients from approximately 150-200 sites (300 physicians) in the Russian Federation. The number of patients enrolled by each physician/site will be limited in order to avoid a situation when 1 large site affects results, thus having a negative impact on the representativeness.

#### **4.3 Study Duration**

The observation period will last from the enrollment in the program during Visit 1 until Visit 3 (Month 6 ±30 days). **Discontinuation of the drug product administration by the patient is not the reason for exclusion of the patient from the study.**

A decision on the duration of treatment is made by the attending physician at his/her discretion in accordance with the valid approved Instruction and the routine clinical practice but this program will include patients who are prescribed Omacor for at least 6 months. It is expected that the enrollment period will be approximately 3 months. The overall duration of the program is about 9 months.

##### **4.3.1 Product Supply**

Since this is a non-interventional observational program and the drug product is prescribed within the frames of a routine clinical practice, Abbott does not provide Omacor. The treatment should be prescribed in accordance with the current Instruction for Medical Use and local recommendations.

##### **4.3.2 Description of Activities**

After enrollment in the program, patients will visit the study site once again to assess their state approximately 3 months and 6 months later. Some of these data will be entered by the patients themselves using their personal account in the electronic system of the program.

## **5.0 Pharmacovigilance-Relevant Information**

### **5.1 Definitions**

#### **5.1.1 Adverse Drug Reaction (ADR)**

The **adverse drug reaction (ADR)** is defined as a response to a medicinal product which is noxious and unintended. In this context, the response means that a causal relationship between the drug product and the adverse event is, at least, rationally possible. Adverse drug reactions may occur as a result of the drug product administration both within the frames of the officially registered Instruction or in the case of the off-label use, or as a result of exposure at the workplace. Cases of the off-label use include administration of the drug product for unregistered indications, overdose, misuse, abuse, and medication errors.

If an adverse drug reaction meets any of the following criteria, it is considered **a serious adverse drug reaction (SADR)**:

**Patient's death** - an adverse reaction that leads to patient's death.

**Life threatening reaction** is an adverse reaction that would lead to the immediate death, on investigator's opinion, if a medical intervention has not been made. This does not include events which would have been fatal in a more severe form.

**Hospitalization** - an adverse reaction that led to admission to the hospital for any period of time. This does not include visits to the emergency departments or outpatient's clinic.

**Prolongation of hospitalization** - an adverse reaction that occurs in a study subject during the hospitalization and prolongs the patient's stay in the hospital.

**Congenital abnormality/malformation** - an abnormality identified at birth or after it, or any defect that leads to the fetal loss.

**Persistent or significant disability/incapacity** - an adverse reaction that leads to a condition which significantly interferes with daily activities of a program participant.

**Important medical event requiring medical or surgical intervention to prevent serious outcome** is an important from a medical point of view adverse event that at first may not be life-threatening or result in death or hospitalization, but, on the basis of a medical conclusion, it may endanger the patient and require medical or surgical intervention to prevent any of the outcomes listed above (for example, the death of the subject, threat to his/her life, hospitalization, prolongation of hospitalization, congenital abnormality/malformation or persistent or significant disability/incapacity). Examples of such events include allergic bronchospasm requiring an

intensive care in the emergency unit or domiciliary, abnormal changes in the blood or convulsions that do not result in hospitalization or the development of drug addiction or drug abuse.

### **5.1.2                   Other Pharmacovigilance- relevant information**

**In the context of this Protocol, “other safety-related data” means:**

- cases related to the exposure of the drug product during pregnancy (related to the mother, the father or the fetus) with the development of an adverse drug reaction or without it;
- transmammary exposure of the drug product on the infant (transmission through the breast milk) with the development of an adverse drug reaction or without it;
- overdose with the development of an adverse drug reactions or without it;
- abuse or misuse (for example, use without clinical reasons) with the development of an adverse drug reaction or without it;
- medication errors (for example, any event that may cause or lead to inappropriate use of the drug product or harm a patient, despite the fact that the treatment is monitored by a healthcare professional, patient, or consumer) with the development of an adverse drug reaction or without it;
- unexpected therapeutic or clinical benefit of the drug product administration;
- any failure in the expected pharmacological effect (for example, “reports on the lack of efficacy”);
- supposed transfer of the infectious agent through the drug product;
- off-label use with the development of an adverse drug reaction or without it;

unintentional, accidental exposure or exposure at the workplace with the development of an adverse drug reaction or without it.

### **5.2                   Serious AE/ADR Collection Period**

Adverse drug reactions, serious adverse drug reactions and other safety-related information will be reported to Abbott from the inclusion of the patient in the program during Visit 1 until Visit 3. All adverse reactions, observed in a patient outside the frames of this program should be reported to regulatory authorities by a physician in accordance with the legislation of the Russian Federation and the local practice of the healthcare institution.

**5.3****Reports on ADR, SADR and other safety-related data**

In the case of an adverse drug reaction, serious adverse drug reaction and reporting of other safety-related data, a physician must notify the contact person in Abbott mentioned below within 24 hours after getting acquainted with this information.

**6.0****Ethics and Quality**

Patient's written consent to the use and/or disclosure of personal and/or medical information must be obtained before his/her inclusion in the program and patients who are not yet ready to express such written consent will not be included in the program. However, all reasonable efforts will be made to avoid the disclosure of personal information (such as name, address, etc.).

The program will be carried out in accordance with the Protocol, principles of the International Conference on Harmonization, ethical standards based on the Declaration of Helsinki, and all applicable local requirements.

As it is known, the main purpose of the observational/noninterventional studies is to obtain information about everyday clinical practice which is not subjected to any external influences. Since it is not always possible to distinguish between "clinical practice" and "intervention", for example, there is still no clear understanding whether the use of questionnaires and patient diaries violates the principle of non-intervention, then the final decision is made by the Ethics Committee [8].

Taking into account the facts mentioned above, the Protocol and relevant documents related to the program will be submitted to the Ministry of Healthcare of the Russian Federation to make a decision to determine the type of study applied in this program; it will also decide whether the requirements of the Russian legislation listed in the Federal law No. 61 "On Drug Circulation" dd April 12, 2010 may be applied to this program.

Program documents will also be submitted to the Independent Ethics Committee (IEC), Intercollegiate Ethics Committee ([name]), and, when necessary, to the Local Ethics Committees (LEC) in the study sites. Enrollment of patients will begin only after receiving a written approval from the IEC.

All data will be collected and processed in a manner that does not disclose the identity of individual patients and, therefore, patient confidentiality will be maintained at any time.

The study doctor will be responsible for ensuring that the quality control and quality control system which ensure the implementation of the program and collection, documentation and reporting in accordance with the Protocol, accepted standards of Good Clinical Practice (GCP) and all applicable local laws and requirements are implemented.

Members of the clinical research team in the Russian branch of Abbott will monitor completeness and correctness of data in electronic CRFs after they have been completed in the EDC. Any discrepancy/contradiction will be brought to the attention of the study site in order to be corrected. All necessary corrections will be entered to the database in accordance with the applicable procedures of the EDC.

## **7.0 Data Analysis Plans**

This section describes the basic information about statistical data analysis within the frames of this observational program.

### **Calculation of a sample size**

The main objective of the program is a research and does not aim at verification of any hypothesis, so no formal sample size calculation has been carried out. It is planned to include 3000 patients in 150-200 centers (300 physicians): this sample size is sufficient for adequate scientific assessment of findings.

### **Population for data analysis**

**Per Protocol Population** will include those patients who have completed at least Visit 2. This population will be used to assess the effectiveness. If the patient discontinues the treatment, the follow-up continues until expiration of 6 months from the date of initiation of Omacor. And for such patients the level of compliance is also calculated.

---

The endpoints which are applicable will be evaluated in subgroups of patients with the different medication adherence rate: <0,5, 0,5-0,7, ≥0,8 at Visit 2 and Visit 3. Adherence rate will be calculated as the sum of days when patient taken the full prescribed dose of Omacor in period divided by the number of days in period.

**Safety Population** will include those patients who have completed at least 1 Visit, i.e. they have been taking Omacor for not less than 3 days. This population will be used for reporting on ADR, SADR, and other safety-related data.

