### **Secondary endpoints**

1. The percentage of patients who have chosen each of the suggested reasons for therapy termination will be determined.
2. The average score on each of 8 scales of SF-36 quality of life questionnaire at Visit 2 and Visit 3 vs. the baseline (Visit 1) will be determined.
3. The average values of lipid profile at Visit 2 and Visit 3 vs. the baseline (Visit 1) will be determined.
4. Number of hospitalizations due to cardio-vascular reasons during 6 months of the program will be determined.
5. Number of new cases of stenocardia within 6 months of the program will be determined.

---

6. Number of cases non-fatal myocardial infarction cases during 6 months of the program will be determined.
7. Number of cases of cardio-vascular death within 6 months of the program will be determined.
8. Mean adherence rate will be determined at Visit 2. Adherence rate will be calculated as the sum of days when patient taken the full prescribed dose of Omacor® in period divided by the number of days in period.
9. Change of mean adherence rate by end of the study (Visit 3) versus Visit 2 will be determined.
10. The percentage of patients with adherence rate  $<0,5$ ,  $0,5-0,7$ ,  $\geq0,8$  will be determined at Visit 2 and Visit 3.
11. Mean score of National questionnaire of treatment compliance (edited by Fofanova T.V. et al.) [9] will be determined at Visit 1, Visit 2.
12. Change of mean score of National questionnaire of treatment compliance (edited by Fofanova T.V. et al.) [9] at Visit 2 and Visit 3 versus baseline (Visit 1) will be determined.

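### Visit 2 completers are the only population named for effectiveness, so on the natural reading CV deaths before about month 3 cannot enter the 6-month death count, and mean adherence describes attenders

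*Combined protocol and SAP*

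**What the plan says.** Section 7.0, Population for data analysis, defines two sets. The Per Protocol Population "will include those patients who have completed at least Visit 2. This population will be used to assess the effectiveness". The Safety Population needs only one completed visit, and its use is given as follows: "This population will be used for reporting on ADR, SADR, and other safety-related data". Section 7.0 also uses all included patients, but only for demographics and baseline characteristics.

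On timing, section 4.3.2 says that after enrolment "patients will visit the study site once again to assess their state approximately 3 months and 6 months later". No window is given for Visit 2. Section 4.3 sets Visit 3 at month 6 ±30 days.

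CV death is a secondary endpoint in section 4.0: "Number of cases of cardio-vascular death during 6 months of the program". Section 7.0 repeats it without naming a population: "Number of cases of cardio-vascular death within 6 months of the program will be determined". Non-fatal MI, new stenocardia and CV hospitalisation are handled in the same way. The objective that these events fit is worded "To evaluate health outcomes in patients group during the program". The primary-endpoint text in section 7.0 names no population for mean adherence either.

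Sections 4.3 and 7.0 keep patients who stop Omacor in follow-up and calculate compliance for them.

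**The concern.** Membership of the effectiveness set depends on surviving and attending for about the first half of follow-up, while the event endpoints are defined over the whole of it. For death the conflict is structural, because a patient who dies before Visit 2 cannot complete it. For adherence the problem is selection: coming back to the clinic is plausibly related to taking the medicine as prescribed.

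The programme tests no hypothesis, so no test is invalidated. Its descriptive counts and means are its results, however. They would stand beside baseline tables on all included patients and be read as applying to those same patients.

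**Working it through.** The plan states no event rate, dropout rate, adherence level or precision target, so it has no figure to reproduce. Its 3000 patients are given without a calculation.

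**Step 1: which population applies to the event counts.**
- Per Protocol: for effectiveness; requires Visit 2.
- Safety: for ADR, SADR and other safety-related data; requires one visit.
- All included patients: for demographics and baseline.

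The CV events are secondary endpoints that fit the health-outcomes objective, and they are not listed as safety data. Per Protocol is the set that fits best, but no text says so.

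**Step 2: whether the Safety Population fills the gap.** For an adverse drug reaction, section 5.1.1 says "the response means that a causal relationship between the drug product and the adverse event is, at least, rationally possible". A CV death not attributed to Omacor is therefore not an ADR. It could surface if reported as a lack of effect under section 5.1.2, but that is not the endpoint count.

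**Step 3: share of CV deaths excluded.** With a constant hazard λ, Visit 2 at month t and follow-up to month T:

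share = (1 − exp(−λt)) / (1 − exp(−λT)) ≈ t/T when risk is low.

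| Visit 2 (t) | End (T) | t/T | Share |
|---|---|---|---|
| 3 | 6 | 3/6 | 50% |
| 2 | 6 | 2/6 | 33% |
| 4 | 6 | 4/6 | 67% |
| 3 | 7 | 3/7 | 43% |
| 3 | 5 | 3/5 | 60% |
| 2 | 7 | 2/7 | 29% |
| 4 | 5 | 4/5 | 80% |

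T = 5 to 7 is the plan's Visit 3 window. t = 2 to 4 is assumed. The level of mortality hardly matters: the exact form with t = 3 and T = 6 gives 0.501, 0.501 and 0.503 at assumed 6-month risks of 0.5%, 1% and 2%. As an illustration in absolute terms, 1% of 3000 is 30 deaths, of which about 15 would be excluded.

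**Step 4: non-fatal events.** An event before Visit 2 is kept if the patient later completes Visit 2. If a share x never completes it and their event rate is r times that of completers, the loss is xr / (xr + 1 − x). With x = 0.10 (assumed), r = 1 gives 0.10, and r = 2 gives 0.20/1.10 = 0.18. This presumes that those events would otherwise have been captured.

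**Step 5: adherence, as illustration only.** If attenders average A, non-attenders average a, and a share x misses Visit 2, the overstatement is x(A − a). With A = 0.80 and a = 0.40 (both assumed):
- x = 0.10 gives 0.10 × 0.40 = 0.04;
- x = 0.20 gives 0.20 × 0.40 = 0.08;
- a = A gives zero.

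A confidence interval would not reveal such a shift. With an assumed SD of 0.25 and 2700 attenders, the 95% half-width is 1.96 × 0.25/√2700 = 0.009.

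**The case against.** The strongest reply is that the plan never calls the event counts effectiveness. The objective speaks of health outcomes, and section 7.0 says only that the numbers will be determined, so an analyst could count events in every included patient without breaching any sentence. This stands in part. A reader might infer that the plan expressly bars early deaths from the count, and it does not. If the natural reading is rejected, though, these endpoints have no stated population at all, and the same paragraph needs the same repair.

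Second, for adherence the population label is not the main mechanism. Both primary endpoints are measured at Visit 3. A patient who never returns has no questionnaire score under any definition and may have no dosing-day record, since section 4.3.2 says only "Some of these data will be entered by the patients themselves using their personal account in the electronic system of the program". This stands: it is largely a missing-data problem, and redefining the set may recover little.

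Third, the programme is single-arm and mainly descriptive. Individual listings are planned, and section 7.0 disclaims formal conclusions from its visit comparisons. This limits the consequence, but listings are not a reported count.

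Other stronger readings are tempting but unsupported:
- Patients who stop treatment are not dropped: those who stop Omacor but attend are retained.
- Early non-fatal events are not all lost.
- An early CV death judged to be drug-related would still appear as an SADR.
- Termination reasons and the 1-month usability rating fit the term effectiveness less well, so I do not rest the point on them.

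**Conclusion.** The point holds in conditional form and should be fixed. It rests on reading the effectiveness set as governing the CV event counts and adherence, which is the best-supported reading but is not stated. On that reading, the exclusion of CV deaths before Visit 2 follows by definition and needs no dropout assumption. Its size, about half with a range of 29-80%, depends on a constant hazard and on when the visits actually fall. It is a share of an unknown number of deaths.

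The loss of non-fatal events is conditional on never completing Visit 2. Mean adherence describes Visit 2 attenders and is probably, not certainly, higher than in all enrolled patients. A reader might infer a known overstatement from the illustrative figures. The documents do not support one, because they give neither dropout nor adherence levels.

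**What to change.** In section 7.0, Population for data analysis:

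1. State that CV death, non-fatal MI, new stenocardia and CV hospitalisation are counted in all enrolled patients from Visit 1. Add that deaths not traced by the site may still be missed.
2. Report the adherence rate in all enrolled patients with any dosing-day data, after confirming which data patients enter themselves. Keep Visit 2 completers as a supportive analysis.
3. Report the number, reasons and baseline characteristics of patients who miss Visit 2 or Visit 3.
4. State that the Visit 3 questionnaire mean applies to attenders.

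Time at risk to last contact is optional. So is a lower-bound adherence analysis that counts days after last contact as not taken; if used, it must be labelled a bound and not an estimate.

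The cost is revised wording and a few extra tables. The adherence figure will probably look less favourable. How much is recovered depends on what data exist for non-attenders: no section describes tracing deaths among them, and only part of the data is self-entered.

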### **Analysis of the primary endpoint**

1. Mean adherence rate will be determined at the end of the study (Visit 3). Adherence rate will be calculated as the sum of days when patient taken the full prescribed dose of Omacor® in period divided by the number of days in period.
2. Mean score of National questionnaire of treatment compliance (edited by Fofanova T.V. et al.) [9] will be determined at the end of the study (Visit 3).

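### Does the undefined adherence period, with a separate follow-up clock for patients who stop Omacor, leave primary endpoint 1 open enough to need a change?

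*Combined protocol and SAP*

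**What the plan says.** The protocol's Primary endpoints section defines the adherence rate as "the sum of days when patient taken the full prescribed dose of Omacor® in period divided by the number of days in period". The same formula recurs wherever the rate appears, each time without a start or end date. Under Analysis of the primary endpoint the time point is Visit 3: "Mean adherence rate will be determined at the end of the study (Visit 3").

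Two places describe how long patients are followed:

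- Section 4.3 applies to everyone: "The observation period will last from the enrollment in the program during Visit 1 until Visit 3 (Month 6 ±30 days"). It adds that "Discontinuation of the drug product administration by the patient is not the reason for exclusion of the patient from the study".
- Section 7.0, Population for data analysis, says of patients who discontinue that "the follow-up continues until expiration of 6 months from the date of initiation of Omacor", and then: "And for such patients the level of compliance is also calculated".

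The rate also feeds secondary endpoint 8 (Visit 2 rate), endpoint 9 ("Change of mean adherence rate by end of the study (Visit 3) versus Visit 2") and endpoint 10 (shares in adherence bands). It also defines the subgroups used for other endpoints: "The endpoints which are applicable will be evaluated in subgroups of patients with the different medication adherence rate".

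**The concern.** A ratio needs a bounded denominator, and this is a primary endpoint. Treatment starts before enrollment: 3 to 17 days before under section 4.1.1, 0 to 14 days before under the amendment's wording. Six months from initiation therefore ends earlier than six months from Visit 1. The sentence giving stoppers the initiation clock is followed directly by one saying that their compliance is calculated, so a programmer could take that clock as their denominator. Stoppers have the lowest rates, and the clock would on average raise them, so the effect would not average out in the mean or in the band percentages.

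Endpoint 9 also needs to know whether the Visit 3 rate accumulates from Visit 1 or restarts at Visit 2. The answer changes both the size of the reported decline and the primary mean.

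**Working it through.** The plan gives no figure to reproduce: it has no formal sample size calculation and no expected adherence, stopping rate or SD.

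**Inputs from the documents.** Visit 3 is at Month 6 ±30 days, which is day 180 with a range of 150 to 210 if months have 30 days. The lead-in *g* before Visit 1 is 3-17 days (midpoint 10), or 0-14 under the amendment (midpoint 7). *n* = 3000.

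**Assumptions.** Visit 2 is on day 90. A share *p* of patients, 10% to 50%, stops on days uniform over 0-180. Intake is 0.9 while on drug. There is no clustering.

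**1. One patient, full intake to day 100, then none.**
- Visit 1 to day 180: 100/180 = 0.556.
- Initiation clock, *g* = 10, earlier days counted: 110/180 = 0.611.
- Initiation clock, *g* = 10, only the end date moved: 100/170 = 0.588.
- Visit 1 to a Visit 3 on day 150 or day 210: 100/150 = 0.667 or 100/210 = 0.476.

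The visit window that the plan openly allows moves this patient further than the clock does.

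**2. Shift in the mean if stoppers alone get the initiation clock, against Visit 1 to day 180.**
- Earlier days counted: *p* × 0.9 × (*g* − *g*²/360)/180.
- Only the end date moved: *p* × 0.9 × *g*/360.
- Model variance: 0.81 × (1 − *p* + *p*/3) − [0.9 × (1 − *p*/2)]². CI half-width: 1.96 × SD/√3000.

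| *p* | *g* = 7, end date only | *g* = 7, days counted | *g* = 10, end date only | *g* = 10, days counted | CI half-width |
|---|---|---|---|---|---|
| 0.1 | 0.002 | 0.003 | 0.003 | 0.005 | 0.006 |
| 0.3 | 0.005 | 0.010 | 0.008 | 0.015 | 0.009 |
| 0.5 | 0.009 | 0.017 | 0.013 | 0.024 | 0.010 |

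Seven of the twelve shifts lie below the half-width. The largest is 0.024.

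**3. Bands.** Place rates between 0.7 and 0.8 in the middle band and take *g* = 10 with earlier days counted. Against day 180, 20 of 180 stop days change band. The lowest band loses 10/180 = 5.6 points of stoppers and the highest gains the same. That is 0.3 × 5.6 = 1.7 to 0.5 × 5.6 = 2.8 points of all patients.

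**4. Direction.** All those moves are upward only because the comparison ends on a fixed day 180, which the plan does not use. With Visit 3 uniform on days 150-210 and *g* = 10, a simulation of 2 million stoppers gives about 15% a lower rate on the initiation clock when earlier days count, and 31% when only the end date moves. The average shift is still upward.

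**5. Cumulative or interval.** A stopper averages 0.9 × 0.5 = 0.45 over days 0-180 and 0.9 × 0.25 = 0.225 over days 90-180.
- *p* = 0.3: 0.7 × 0.9 + 0.3 × 0.45 = 0.765, against 0.63 + 0.3 × 0.225 = 0.6975. Gap 0.0675.
- *p* = 0.5: 0.45 + 0.225 = 0.675, against 0.45 + 0.1125 = 0.5625. Gap 0.1125.
- *p* = 0.1: 0.855 against 0.8325. Gap 0.0225.
- Endpoint 9, for a fall from 0.90 before Visit 2 to 0.60 after it: cumulative (0.90 + 0.60)/2 − 0.90 = −0.15; interval −0.30.

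**6. What the text supports.** The only observation period that the plan defines for all patients is Visit 1 to Visit 3, and stoppers are explicitly kept in it. The primary rate is taken at its end. Following stoppers on and calculating their compliance makes sense only if days after the last dose count as not taken, so a denominator cut at the last dose is excluded. The last-day rule under Experimental endpoints belongs to the count of days on drug. The section 7.0 sentence therefore reads as a loose restatement that stopping does not end follow-up.

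**The case for a change.** The strongest case for a change rests on cumulative versus interval, not on the two clocks. At 30-50% stopping that choice moves the primary mean by 0.07 to 0.11, which is 0.0675/0.0090 = 7.5 to 0.1125/0.0104 = 10.8 times the half-width. In a descriptive study the estimate is the result, so its denominator should be fixed before anyone sees data, and the adherence subgroups inherit whatever is chosen.

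The silence is real, and so is the size if the interval reading were taken. But that reading would make an end-of-study adherence rate ignore the first half of the study, and no text suggests that the count restarts at Visit 2. Read cumulatively, endpoint 9 is simply the Visit 3 rate minus the Visit 2 rate, as it is worded.

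A fuller rule would not clearly improve matters. Truncating at day 180 discards data that the visit window permits. Computing endpoint 9 from separate intervals while keeping the primary rate cumulative would report −0.30 beside two rates that differ by −0.15. Filling in zeros only for recorded stops still leaves patients whose data end early. One with a 0.9 rate and data only to day 90 could lie anywhere from 81/180 = 0.45 to 171/180 = 0.95, a far wider range than the clock effect.

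**Conclusion.** No change to the plan follows. The plan does not bound the period, and its two follow-up statements start from different dates. However, they can coexist as visit scheduling, neither sets a denominator, and Visit 1 to Visit 3 with days after stopping counted as not taken is the reading a competent analyst would adopt.

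If the initiation clock were used for stoppers instead, the mean would rise by about 0.002 to 0.024. That rests on an assumed lead-in of 7-10 days, 10-50% stopping, uniform stop days and 0.9 intake. More than half of the cases computed fall below the confidence half-width, and the direction varies between patients. The cumulative or interval choice would matter more (0.07 to 0.11 at 30-50% stopping), but the text favours the cumulative rate.

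The program tests no hypothesis, and its SAP text says that no formal conclusions follow from its comparisons. The questionnaire endpoint and patients with constant adherence are unaffected. This is missing detail, not a flaw in the analysis.
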